### 9.3.2 Interim Analysis and Multiple Testing

[REDACTED]

[REDACTED]

[REDACTED]

	[REDACTED]	[REDACTED]	[REDACTED]
	[REDACTED]	[REDACTED]	[REDACTED]
[REDACTED]	[REDACTED]	[REDACTED]	[REDACTED]
[REDACTED]	[REDACTED]	[REDACTED]	[REDACTED]

[REDACTED]

[REDACTED]

[REDACTED]

[REDACTED]

[REDACTED]

### 9.3.3 Analysis Sets

#### 9.3.3.1 Full Analysis Set (FAS)

The Full Analysis Set (FAS) will be used for all efficacy analyses and is defined as all patients who are randomised to treatment; patients in this population will be analysed according to the treatment to which they were randomised. All available data for PFS and survival will be collected and analysed for these patients. For FAS patients who have inadequate data post-baseline to assess efficacy according to the criteria for response or who dropped out before EOS, follow-up will be censored for

analysis of PFS on the date of the last adequate tumour assessment prior to withdrawal (see the Statistical Analysis Plan [SAP] for more details).

The confirmatory analysis of the primary and the 2 key secondary endpoints will be based on the FAS.

#### **9.3.3.2 Per Protocol set (PP)**

In order to determine if any bias results from including untreated patients or patients lost to follow-up in the primary FAS analysis, an additional analysis will be conducted on patients who are protocol-compliant: the Per Protocol set (PPS). Patients with major protocol violations determined before statistical analysis will be excluded from this population. Major protocol violations are defined as those that could impact the efficacy or safety evaluations and will be specified in the SAP. For the study arms the following deviations are defined as major protocol deviations, leading to exclusion from the PPS:

- Lu-edotreotide arm:
  - Subjects with incomplete Lu-edotreotide infusion, in which less than 50% of the total pre-scribed activity (GBq) based on initially dosimetry assessment was injected.
  - Subjects missing more than two scheduled doses, or in whom dose were administered more than 30 days outside the date, specified per protocol.
- Everolimus arm:
  - Subjects missing more than 14 doses, within a visit interval of 30 days (with exception of treatment interruptions due to toxicity (see Section 5.4.3.1)).

#### **9.3.3.3 Safety Analysis Set (SAF)**

All patients who received at least one dose of any study treatment will be included in the Safety Analysis Set (SAF). Patients will be analysed according to the treatment they actually received. Analyses of safety parameters will be based on the SAF.

#### **9.3.3.4 Other Populations**

In case of specific assessments in specific groups of patients, analyses will only be conducted in the appropriate group of patients where relevant. As an example, the analysis of substudy variables will only be analysed based on the population of patients who actually participated in the corresponding substudy.

#### **9.3.4 Statistical Analyses**

The detailed procedures for data analysis are described in the Statistical Analysis Plan (SAP), which will be defined before start of statistical evaluation. Any changes in the original statistical methodology will be documented in the SAP.

Statistical analyses will be performed after the data base has been appropriately locked (See Section 9.3.2).

All data from the CRF and other study documents will be reported in listings. Continuous parameters will be summarised using descriptive statistics (number, mean, standard deviation, minimum, median, maximum) and categorical parameters will be summarised using frequency tables. Corresponding 95% confidence intervals will be presented additionally where meaningful.

Statistical hypothesis testing of the primary variable and the key secondary variables will be performed maintaining an overall Type I Error (alpha) of 5% (two-sided).

Multiplicity will be accounted for by adhering strictly to the described interim analysis and hierarchy testing plan with regard to the primary and the key secondary endpoints (see Section 9.3.2).

Exploratory statistical hypothesis tests will be used at a significance level of 0.05 (two-sided), and considered at a purely descriptive level.

Withdrawals and protocol deviations will be listed. Missing data that cannot be obtained will not be substituted, unless stated otherwise (see SAP for more details). A given data set entry is presumed to be an outlier if the value is evidently contrary to generally accepted data. Such occurrences will be recorded. Results from analyses excluding outliers may be explored by comparing to results based on the complete data set; differences will be discussed.

[figure not shown]
All statistical evaluations, including graphical data summaries, will be performed using appropriate software.

## **9.4 Determination of Sample Size**

Considering that everolimus will be used as comparator in the planned study, a sample size estimation was conducted, based on a median PFS of 11.0 months reported for everolimus (Yao et al., 2011, 2016). and a median PFS of 32 months in NET patients (34.5 in GEP-NET patients), as determined for Lu-edotreotide in subjects treated with ≥2 PRRT cycles in the retrospective study (van Echteld 2015, Baum et al., 2016).

[REDACTED]

[REDACTED]

**Figure 4: PFS for everolimus and  $^{177}\text{Lu}$ -edotreotide in NET**

Kaplan Meier estimates of PFS, reported for everolimus (blue), and  $^{177}\text{Lu}$ -edotreotide ( $\geq 2$  cycles; green), in patients with NET (N=32)

Figure 4 shows the Kaplan Meier estimates of PFS reported for everolimus (Yao et al., 2011) and  $^{177}\text{Lu}$ -edotreotide (van Echteld et al., 2015; Baum et al., 2016) in NET patients.

A prolongation of mPFS by  $\geq 6$  months, compared to comparator is already considered a relevant clinical benefit, constituting superiority over existing treatments in patients with advanced GEP-NET. To visualise, the dotted blue curve in Figure 4 is a simulated curve representing this mPFS benefit of 6 months, which shows a difference of 25% in PFS at 11 months.

For the sample size calculations, i.e. estimating the sample size, the power and/or the effect size, the following considerations were taken into account:

[REDACTED]. Study duration per patient will be 30 months. The accrual across time is uniform. Of note, the trial sample size was not revised (i.e. decreased) after the protocol amendment that extended the patient follow-up from 24 months to 30 months.

Based on this HR a total sample size of 300 will compensate for a dropout rate (censored data) of 15% for primary endpoint analysis. Switching from the one group to the other is not allowed in this study and therefore not considered in the sample size calculation.

With regard to overall response rates, group sample sizes of 200 in the  $^{177}\text{Lu}$ -edotreotide group and 100 in the everolimus group achieve █% power to detect an odds ratio between the group ORRs of █ (that corresponds to rates of █% and █%). The proportion in the  $^{177}\text{Lu}$ -edotreotide group is assumed to be █% under the null hypothesis and 18% under the alternative hypothesis. The proportion in the everolimus group is assumed to be 5% according to results of the RADIANT-3 study (Yao et al., 2011). The test statistic used is the two-sided Fisher's Exact Test. The significance level of the test is 5%. A dropout rate of 15% is included in this calculation using PASS software.

With regard to overall survival, a two-sided logrank test with an overall sample size of N=300 subjects (█ events; █, N1=100 subjects █] in the everolimus group and N2=200 subjects █ events] in the  $^{177}\text{Lu}$ -edotreotide group) achieves █ power at a █ significance level to detect a hazard ratio (HR) of █ when the everolimus group median overall survival time is 44 months as in the RADIANT-3 study (Yao et al., 2016) (i.e., a difference of an additional 23 months in the  $^{177}\text{Lu}$ -edotreotide group). The observation time for overall survival will be 5 years (60 months) after EOS for all patients.

The sample size of 300 patients was chosen as the primary endpoint and the 2 key secondary endpoints are to be tested in a confirmatory manner. This sample size allows to address historically assumed PFS treatment effect (which would require █ events) and minimal clinically relevant PFS difference (which would need █ events).

█  
█  
█

- █  
█
- █
- █

In conclusion, the trial sample size of 300 randomized patients associated with the interim analysis plan will allow to cover all the possible treatment effect assumptions (minimal, expected and historical) at an overall two-sided level of significance of 0.05 and with acceptable power (i.e. █).

The sample size estimation was performed using SAS, PASS Power Analysis and Sample Size Software (version 13).

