## **11.2 Independent Data Safety Monitoring Board**

An independent data safety monitoring board (IDSMB) will review safety data at regular intervals throughout the study. If there are any signs of safety issues, the IDSMB may suggest terminating the trial.

Corresponding to the previously described toxicity pattern for PRRT agents (IAEA PRRT monograph 2013), the IDSMB will put special emphasis on identifying possible acute and delayed radiotoxic effects which are predominantly expected for bone marrow and kidneys.

To identify relevant safety issues in a timely fashion, the IDSMB will perform an ongoing review of SAE notifications, deaths, instances of DMT (see Section 5.4.3.2), instances of patients not meeting the pre-defined eligibility criteria for continued administration of Lu-edotreotide after cycle 1 (see Section 5.4.1.2), or other toxicities requiring discontinuation of Lu-edotreotide treatment in the opinion of the investigator, as well as other AEs of interest (e.g. creatinine values). The IDSMB will prepare summary reports with safety assessments and recommendations. For the first 36 PRRT patients, the IDSMB will review 3 consecutive cohorts of 12 PRRT patients who have reached the day 90 (±14) day evaluation (i.e. baseline for cycle 2), allowing to characterise a representative safety profile at the end of this treatment cycle, but will also consider any available additional data from patients who have already advanced beyond cycle 1 at the time of review. After the first 36 PRRT patients, the IDSMB will convene in 6-monthly intervals. Details will be described in the IDSMB charter.

Results of previous trials have shown that Lu-edotreotide has the potential to perform considerably better than current standard therapy (Baum et al., 2016). Therefore, termination for futility was not considered. Patients who experience progression under everolimus may switch to treatment with Lu-edotreotide off-study at the discretion of the Investigator (see Section 7.4.2).

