3.1 General Study Design and Plan

Phase: III, multi-centre

Study configuration and experimental design: confirmatory, prospective, parallel group

Type of control: active drug

Blinding: open-label

Treatment assignment: 300 GEP-NET patients randomised in a 2 : 1 fashion to receive either

- PRRT with ^{177}Lu -edotreotide consisting of a maximum of four cycles (7.5 ± 0.7 GBq ^{177}Lu -edotreotide, each), administered as IV infusion at 3-monthly intervals for 9 months, or until diagnosis of progression (200 patients), or
- 10 mg everolimus (Afinitor®) daily, administered orally as a tablet (100 patients).

Duration: Baseline: day -90 to -1

Randomisation: day -28 to -1

Treatment and study procedures: month 0 to 30, or until progression or withdrawal – whichever occurs earlier

EOS: month 30 or at progression or drop-out - whichever occurs earlier

Collection of survival and local disease progression data as well as information on further tumour treatments will be continued after EOS during the long-term follow-up.

Please refer to Section 3.1 of the current protocol for more details.

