With regard to overall survival, a two-sided logrank test with an overall sample size of $N=300$ subjects (198 events; randomised 1 : 2, $N_1=100$ subjects [76 events] in the everolimus group and $N_2=200$ subjects [122 events] in the ^{177}Lu -edotreotide group) achieves 80% power at a 5% significance level to detect a hazard ratio (HR) of 0.660 when the everolimus group median overall survival time is 44 months as in the RADIANT-3 study (Yao et al., 2016) (i.e., a difference of an additional 23 months in the ^{177}Lu -edotreotide group). The observation time for overall survival will be 5 years after EOS for all patients. The study duration was planned to last 48 months during which patient recruitment would take place in the first 24 months. The post-study follow-up period will then continue for another 5 years (60 months).

The sample size of 300 patients was chosen as the primary endpoint and the 2 key secondary endpoints are to be tested in a confirmatory manner. This sample size allows to address historically assumed PFS treatment effect (which would require 31 events) and minimal clinically relevant PFS difference (which would need 180 events).

In case a difference of 11 months in median PFS is observed ($m_1=11$ months versus $m_2=22$ months) the sample size also allows confirmation of PFS improvement for ^{177}Lu -edotreotide relative to reference treatment. This would need a total number of:

ITM-LET-01	Statistical Analysis Plan
-------------------	----------------------------------

- 205 events (E1=84 events in the everolimus group and E2=121 events in the ¹⁷⁷Lu-edotreotide group) with a power of about 99% and a two-sided level of significance of 1%
- or 156 events with a power of about 99% and a two-sided level of significance of 5%.
- or 67 events with a power of about 80% and two-sided level of significance of 5%.

In conclusion, the trial sample size of 300 randomized patients associated with the interim analysis plan at 90, 135 and 180 events (See Section 5.7) will allow to cover all the possible treatment effect assumptions at an overall two-sided alpha of 0.05 and with acceptable power (i.e. ≥80%; see Table 2).

Table 2: summary of PFS primary endpoint sample size assumptions

	Minimal clinically relevant difference	Historical treatment effect	Expected treatment effect		
Median PFS IMP	17	30	22		
Median PFS control	11	11	11		
Number of PFS events needed	180	31	67	156	205
Sample size (2:1)	242 (300 with dropout rate)	51	300		

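### The stated 80% overall-survival power has no allowance for switching and assumes longer follow-up than the plan's own rule gives; it should be restated as a conditional range

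*Protocol*

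**What the plan says.** **The OS power.** SAP section 4 (Sample Size) reads "With regard to overall survival, a two-sided logrank test with an overall sample size of" 300, with "198 events; randomised 1 : 2", split as 100 "subjects [76 events] in the everolimus group" and 200 subjects with 122 events in the 177Lu-edotreotide group. This design "achieves 80% power at a 5% significance level to detect a hazard ratio (HR) of 0.660", with a control median of 44 months. Protocol 9.4 carries the same paragraph with most figures blacked out, so the SAP figures are used here.

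**Follow-up.** The SAP adds: "The observation time for overall survival will be 5 years after EOS for all patients". Beside this it describes a 48-month study with recruitment in the first 24 months, followed by another 60 months. SAP 3.1 defines "EOS: month 30 or at progression or drop-out - whichever occurs earlier". Protocol 4.6 agrees for the individual patient, and Protocol 7.4.1 counts the five years from each patient's own end of study.

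**Switching.** Protocol 9.4 states "Switching from the one group to the other is not allowed in this study and therefore not considered in the sample size calculation". The sentence comes straight after the 15% dropout allowance for the primary endpoint and before the OS paragraph; SAP section 4 omits it. Protocol 11.2 states "Patients who experience progression under everolimus may switch to treatment with" 177Lu-edotreotide off study, at the investigator's discretion. Protocol 7.4.2 lets the investigator request the drug from the sponsor, and SAP section 17 describes a rollover extension in France.

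**Handling in the analysis.** SAP 3.4.2 and section 6 apply when at least 33% of the control arm starts new anticancer treatment or receives PRRT. The main OS analysis then treats treatment as time-dependent, with RPSFT, intention-to-treat (ITT) and censoring at switch as sensitivity analyses. Protocol 9.3.1 is softer: the analysis may take switches into account, with more than 33% receiving PRRT as the example.

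**The concern.** OS is tested confirmatorily after PFS and ORR, so its stated power should describe the trial as written. Two provisions work against it.

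- **Follow-up.** Because EOS comes at progression, a patient who progresses at month 3 is followed to month 63, not month 90. Fewer deaths are observed than the event count implies.
- **Switching.** If control patients who progress receive the experimental treatment and benefit from it, an ITT comparison of survival is diluted. The power calculation has no term for this.

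A reader of SAP section 4 would take 80% as the chance of detecting a hazard ratio of 0.660. If the real figure is materially lower, a non-significant OS result would carry less information than the plan suggests.

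**Working it through.** **Inputs.** From SAP section 4: N = 300 (100 + 200), HR 0.660, two-sided 5%, control median OS 44 months (so 44/0.66 = 66.7 months in the other arm), PFS medians 11 and 17 months. From SAP 3.1 and section 4: EOS at month 30 or at progression, then 60 months. Exponential times throughout.

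**1. The plan's power.** Schoenfeld: z = √(198 × 1/3 × 2/3) × |ln 0.66| − 1.96 = 6.633 × 0.4155 − 1.96 = 0.80, giving 78.7%. Using the arm-specific events, |ln 0.66| / √(1/76 + 1/122) − 1.96 = 0.88, giving 81.2%. The stated 80% is reproduced.

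**2. The plan's event split.** At a fixed 90 months (30 + 60):
- everolimus: 100 × (1 − 2^(−90/44)) = 75.8
- 177Lu-edotreotide: 200 × (1 − 2^(−90/66.7)) = 121.5

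These round to 76 + 122 = 198. The worded plan (24-month uniform accrual, 48 + 60 = 108 months in total, so 84 to 108 months per patient) gives 77.8 + 126.1 = about 204. The stated count does not match the wording beside it.

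**3. The written follow-up rule.** Potential follow-up is min(time to progression, 30) + 60. The mean of min(T, 30) is (m/ln 2)(1 − 2^(−30/m)) for median m:
- everolimus: 15.87 × (1 − 0.151) = 13.5, so 73.5 months
- 177Lu-edotreotide: 24.53 × (1 − 0.294) = 17.3, so 77.3 months

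Simulated trials (2,000–4,000 per scenario; PFS–OS correlation 0 to 0.8; 177Lu-edotreotide PFS median 17, also 22 and 30) gave about 178–186 deaths and 75–79% log-rank power with no loss and no switching. A fixed 90 months for all gave about 81%. Adding an assumed 15% loss to survival follow-up lowers the no-switch power to about 73–74%.

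**4. Switching.** The documents give no rate and no post-switch effect, so both are assumed. The share is of the whole everolimus arm. Switching occurs at progression before month 30. The remaining survival time is then divided by 0.66 (full benefit) or by 0.66^0.5 (half the log-HR). Follow-up is as in step 3.

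| Assumed share switching | ITT log-rank power, full benefit | Half benefit |
|---|---|---|
| 0% | 75–79% | 75–79% |
| 10% | 68–72% | about 73% |
| 20% | 58–63% | 67–69% |
| 33% | 46–51% | 61–66% |
| 50% | 32–37% | 53–56% |

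The denominator matters. In one check, 33% of eligible progressors was about 23% of the arm and gave 54%; 33% of the whole arm gave 47%. The SAP trigger is a share of the control arm, so that denominator is used here.

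**The case against.** **The plan already deals with switching.** At 33% or more, the ITT log-rank is no longer the main OS analysis. This stands, and it means the ITT figures in the 33% and 50% rows describe a sensitivity analysis. In a rough check (1,000 simulated trials per scenario, PFS and OS independent), a time-dependent test kept about 69% (33% of the arm) and 62% (50%) with full post-switch benefit, against 47% and 32% for ITT. It was similar to ITT with half benefit, and gave 58% and 45% if switching brought no benefit. All are below 80%, and the SAP states no power for that model. Below the trigger the log-rank stays the main analysis.

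**The switching sentence is about PFS.** This also stands. Its position, and the words limiting it to in-study switching, make it defensible there: treatment after progression comes after the PFS event. A reader might infer that the protocol forbids what it elsewhere offers, but the offer applies after study participation ends. The fault is that the sentence speaks of the sample size calculation without limit, in a section that also powers OS.

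**A flat figure of 40–55% power.** A reader might infer this. The documents do not support it: it requires an assumed switching rate and full post-switch benefit.

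**90 months is an inference.** Correct. A 24-month accrual with 102.5 months in total gives 75.8 + 121.7, the same rounded split.

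**Progression-dependent follow-up as a source of bias.** With no OS effect but a PFS effect, simulation moved the hazard ratio only to 1.01–1.02. Dependent censoring is not a material part of this point.

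**OS is last in the hierarchy.** It is, and Protocol 3.3 chose PFS because later treatments make OS hard to interpret. That lowers the severity but does not make the stated power right.

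**Conclusion.** The point holds as a mis-stated planning figure for a confirmatory secondary endpoint. The 80% and the 198 deaths fit about 90 months for every patient with no loss and no switching. The wording beside them implies about 204 deaths, and the written rule delivers about 178–186 deaths and 75–79% power. The follow-up rule alone therefore costs only a few points.

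The larger loss comes from switching and can be given only conditionally. Over assumed shares of 10% to 50% of the everolimus arm, ITT log-rank power runs from about 68–72% to 32–37% with full benefit; with half benefit it is about 53–56% at 50%. Every switching scenario computed is below 80%. These results rest on exponential times, the SAP's PFS and OS medians, switching at progression, and the assumed post-switch effects. At or above the 33% trigger they apply to a sensitivity analysis.

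This should be corrected, but it does not touch the primary PFS inference or the type I error.

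**What to change.** 1. In SAP section 4 and Protocol 9.4, restate the expected deaths and OS power under the rule of EOS plus 60 months, and reconcile this with the 48 + 60-month wording.
2. Give OS power as a range by switching rate, with the whole control arm as denominator and the post-switch benefit stated as an assumption. Do this for both the log-rank test and the time-dependent model that becomes the main analysis at 33%.
3. Limit the sentence that switching is not allowed to the PFS calculation.

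The cost is text edits, a modest simulation and a less favourable stated power.

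Optional: follow survival to a common horizon from randomisation, or to a common calendar cut-off, for every patient. This recovers only about 3–5 points of power and adds up to 30 months of 6-monthly contacts for early progressors.

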## **10 Data Handling and Quality Assurance**

### **10.1 Data Recording**

#### **10.1.1 Case Report Form (CRF)**

For this study patient data will be entered into a sponsor defined eCRF, transmitted electronically to the sponsor or designee and combined with data provided from other sources in a validated data system. The case report form will be supplied for recording all study data from each patient. It is the responsibility of the investigator to ensure that the CRFs are completed in full. All data therein must be supported by source documentation at the study centre. The completion of study page of the CRF must be signed by the principal investigator at the end of the study confirming that he/she is satisfied with its completion and accuracy. A CRF must be completed for every patient who signed an informed consent. The eCRFs must be kept up-to-date so that they always reflect the latest observations on the patient.

Study monitors must never write in the CRF (except to write queries).

In all cases, subject initials or personal data will not be collected by or transmitted to the sponsor or the coordinating CRO.

